#### **Use of Samples and Data:**

Any excess sera collected under this protocol may be coded and stored in the REU lab. Each sample will be given a unique identifying code and may be used for future research. Use of these specimens will be targeted at furthering our understanding of reproductive disorders and improving the management of subjects with these disorders and may include improving existing assays as well as developing new assays. IRB approval will be obtained if samples are used in the future for purposes not described in the protocol.

Samples may be shared with third parties, scientific collaborators, and laboratories. Study data may be shared with scientific collaborators at academic centers. Each collaboration will be driven by clear reproductive research questions and reviewed to ensure the proposed use is consistent with our consent form. When samples or data leave MGB, identifying information will be removed and samples/data will be coded using a unique identifying number. Identifiable data of subjects may be shared with other MGB investigators. Data will be sent to collaborators via secure methods such as secure email or secure file transfer.

Study data may be collected electronically (including via direct data entry into REDCap) or on paper. Electronic information will be stored on secure MGH provided storage systems. Passwords are required to access the information. Paper records are stored in the secure REU, which has restricted access, in double-locked file cabinets/rooms or stored at an offsite storage facility; paper records will also be scanned and stored electronically. After paper records are converted to electronic records the paper copy may be destroyed in compliance with MGB guidance on Electronic Storage of Research Documents. Ongoing access to data is restricted to members of the research team and access to identifiable information is restricted based on staff responsibilities.

Analysis performed under this study may be informed by data collected under other REU studies. All data from this study may be used for ongoing and future research and to better our understanding of reproductive disorders.

#### **VI. BIOSTATISTICAL ANALYSIS**

#### **Assays**

Given the long-term ongoing nature of this study, the assay methodologies employed to characterize the biochemical profile (both reproductive and metabolic) will be based on standard accepted methods as established by the MGH Pathology department and the Reproductive Endocrine Reference Laboratory. As such these methods may include immunoassays, measurement using standard laboratory platforms, radioimmunoassays, and mass spectroscopy. We anticipate that these methods will continue to evolve as the diagnostics field changes.

#### STATISTICAL DESIGN AND POWER

Individuals recruited from the Biobank will undergo baseline neuroendocrine LH pulse pattern evaluation, as well as Kisspeptin and GnRH stimulation testing. Boys and girls with delayed puberty have kisspeptin-stimulated GnRH induced LH pulse amplitude 70% lower than healthy men and luteal phase women (144-145, 147). Therefore, we conservatively estimated a 50% reduction in kisspeptin-stimulated GnRH induced LH pulse amplitude in individuals at highest genetic risk compared to those at lowest risk. To detect a 50% decrease in the LH amplitude, 25 participants in each group would be required to provide a statistically meaningful result (80% power, one-sample exact binomial test). Therefore, the study would enroll 25 individuals (males and females combined) in the high risk group and 25 individuals (males and females combined) in the low risk group for a total of 50. To allow for a 15% estimated drop-out rate, 60 participants (males and females combined) will be enrolled.

The hypotheses will be accepted if subjects at high genetic risk demonstrate reduced endogenous and exogenous kisspeptin-induced LH pulse amplitude compared to individuals at low genetic risk.

Since healthy men and women in the luteal phase have similar responses to exogenous kisspeptin (144, 145), an interim analysis is planned to ensure that this remains true in men and luteal phase women in this study. If it is not the case, then the study would enroll 50 individuals (males and females combined) in the high risk group and 50 individuals (males and females combined) in the low risk group for a total of 100. This possibility is accounted for in study recruitment and analysis.

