#### **Hypotheses:**

Patients with a positive but comparatively attenuated response to kisspeptin will have defects in GnRH neuronal fate specification or migration that reduce either the total complement of GnRH neurons or the coordinated activity of the GnRH neuronal population (e.g. mutations in the genes encoding fibroblast factor receptor 1 [FGFR1]).

Individuals ascertained from the MGB Biobank with rare variants in genes that have been linked to reproductive axis function will have attenuated endogenous LH pulse amplitude or pulse frequency.

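### The high- versus low-risk comparison of LH pulse amplitude combines men and women with no sex term stated, and the check that is meant to justify this does not cover endogenous amplitude

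*Combined protocol and SAP*

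**What the plan says.** Statistical Design and Power sets the base case at "25 individuals (males and females combined) in the high risk group and 25 individuals (males and females combined) in the low risk group", 50 in all, raised to 60 for drop-out. The only test it attaches to amplitude is in the sample-size sentence: "80% power, one-sample exact binomial test". The hypotheses are to be accepted if "subjects at high genetic risk demonstrate reduced endogenous and exogenous kisspeptin-induced LH pulse amplitude compared to individuals at low genetic risk", so the rule has an endogenous half and a kisspeptin-induced half.

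The reason given for combining the sexes is this: "Since healthy men and women in the luteal phase have similar responses to exogenous kisspeptin". It is followed by "an interim analysis is planned to ensure that this remains true in men and luteal phase women in this study". If the check fails, the plan is to enlarge: "If it is not the case, then the study would enroll 50 individuals (males and females combined) in the high risk group", with the same number at low risk, 100 in total. The section then says: "This possibility is accounted for in study recruitment and analysis".

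Data Analysis defines how LH pulses and their amplitude are derived. The one comparison model it names, a repeated-measures analysis of variance, is for FSH and sex steroids. Enrollment Targets gives 60 men and 60 women so that 50 of each complete. These totals are not divided by risk group.

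**The concern.** Sex is an obvious candidate to explain part of the spread in LH pulse amplitude, and the plan itself treats a sex difference as possible. If there is one, leaving sex out of the comparison puts that variation into the error term and costs power. If the proportion of men also differs between the risk groups, the sex difference leaks into the estimated genetic effect. The groups are formed by genotype, and nothing in the plan balances sex within them.

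The plan's safeguard is the interim check, but that check covers less than what is being combined. It concerns the response to exogenous kisspeptin. A fully successful check would say nothing about whether men and women have similar endogenous amplitude, which is the other half of the acceptance rule. The Hypotheses section also has an endogenous hypothesis, that Biobank carriers "will have attenuated endogenous LH pulse amplitude or pulse frequency". That is weaker support, since it allows frequency as an alternative and does not mention the high- and low-risk groups.

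**Working it through.** **1. The plan's own figure.** The 25 per group cannot be re-derived. Alpha, sidedness and the two binomial proportions are not given, and a 50% fall in a mean is not a binomial parameter. Exact one-sample binomial power at n = 25 depends on what is assumed:

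- 0.50 versus 0.75: 72.7%
- 0.60 versus 0.30: 90.2% at one-sided 0.05, or 81.1% at one-sided 0.025

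The drop-out step does reproduce closely: 50/0.85 = 58.8, so 59 against the stated 60. With no usable model in the plan, the sex question has to be sized with an assumed one.

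**2. What is combined against what is checked.**

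| Amplitude | In the acceptance rule | Sex similarity claimed | Checked at interim |
|---|---|---|---|
| Kisspeptin-induced | yes | yes | yes |
| Endogenous | yes | no | no |

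This table needs no outside figure. The claimed similarity is cited to items 144 and 145, while the reference list ends at 59, so the premise cannot be verified from the documents.

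**3. Assumptions for the illustration.** From the plan: 25 per group and a 50% reduction. Not in the plan: two-sided 5%, analysis on log amplitude, and a sex difference of 1.5- or 2-fold. The SD is back-solved so that 25 against 25 gives 80% power for ln 2 = 0.693 (noncentral t). This gives a log SD of 0.857, and the check is 0.693/(0.857 × √(2/25)) = 2.86. The 50% effect is stated for kisspeptin-stimulated amplitude only, so nothing below quantifies the endogenous half.

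**4. Power with sex falling at random (half men), 2-fold difference.** An omitted 50:50 sex factor adds 0.25 × 0.693² = 0.120 to the variance.

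- If 0.857 is the within-sex SD, the unadjusted SD is √(0.734 + 0.120) = 0.924. The standardised difference falls to 0.693/(0.924 × 0.283) = 2.65. Simulated power is about 74% unadjusted and 79% adjusted.
- If 0.857 is the pooled SD, with sex variation already in it, the within-sex SD is √(0.734 − 0.120) = 0.784. Simulated power is about 80% unadjusted and 86% adjusted.

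On the within-sex reading, other assumptions give:

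| Log SD | Sex difference | Unadjusted | Adjusted |
|---|---|---|---|
| 0.857 | none | 80% | 79% |
| 0.857 | 1.5-fold | 78% | 79% |
| 0.6 | 2-fold | 94% | 98% |
| 1.2 | 2-fold | 48% | 51% |

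**5. Type I error.** With sex at random and a 2-fold difference, it is about 5% with or without the sex term. In a realised split of 15:10 against 10:15 men to women (2-fold, within-sex SD 0.857), it is about 6.5% unadjusted and 5% adjusted. Power for a true halving is then 55% or 89% unadjusted, depending on which group has more men, against 78% adjusted. If each participant is equally likely to be male or female, two groups of 25 differ by 5 or more men with probability 0.203.

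**The case against.** The strongest reply is that the plan has foreseen a sex difference. It doubles the study if one appears, sets a target of 50 men and 50 women completing, and says the analysis allows for this. With 100 participants in four cells, 100/4 = 25 per sex per risk group, the same 25 used for 80% power. On that reading the fallback exists to permit sex-specific comparisons, and the wording about combined sexes is a headcount. This largely stands as a reading. A reader might infer that the plan commits to an unadjusted pooled analysis even at 100, and the documents do not support that. They also do not state any analysis for that case. The 25 per cell would need sex balance within risk groups, which the overall totals do not secure. The fallback is also triggered only by the exogenous response.

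A second reply is that the gain is small and assumed. That stands. A reader might also infer from the 74% that the planned 80% is lost. The plan's 25 already covers both sexes, so the implied SD can equally be the pooled one, and then unadjusted power stays near 80%. A further tempting inference is that the test is invalid. It is not, if sex falls at random. The excess error belongs to particular uneven splits.

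A third reply is that no two-group test of LH amplitude is named at all, which is the larger gap. This is true, but whatever test is written in should carry the sex term.

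**Conclusion.** The point holds as a nearly free improvement. The plan describes the risk comparison with the sexes combined and states no sex term for LH pulse amplitude. Its only support for combining them does not reach the endogenous half of its own acceptance rule. That textual gap rests on no assumption.

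The statistical size is illustrative. Adjustment is worth about 5 to 6 points of power under a 2-fold sex difference at 25 per group, about 1 point at 1.5-fold, and costs about 1 point if there is no difference. It also protects against a realised imbalance. These figures rest on an assumed alpha, scale, SD and sex difference, and apply to kisspeptin-induced amplitude only.

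Two neighbouring gaps are separate and do not carry this point. The interim has no stated criterion for enlargement. The Inclusion Criteria, Screening and TCRC Visit sections give no cycle phase for women, although the power section refers to luteal-phase women in the study. A sex term would not remove cycle-phase differences.

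**What to change.** State that the high- versus low-risk comparison of LH pulse amplitude, endogenous and kisspeptin-induced alike, is adjusted for sex at either sample size and whatever the interim shows. A linear model on log amplitude with risk group and sex would do. If some amplitudes are zero, use a rank test stratified by sex. Balance sex within each risk group as far as recruitment allows. If sex-specific comparisons are intended at 100, say so and name them. Let the interim bear only on whether to enlarge, so that a passed check is not taken as grounds for dropping the sex term.

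The cost is some wording and one degree of freedom, about 1 point of power (80% to 79% in the illustration) if the sexes do not differ. The adjustment itself needs no extra participants or procedures, and sex is already recorded.

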# What does the Discovery of Kisspeptin Mean from a Physiologic Perspective? Probe of the GnRH Neuron

Because kisspeptin is a powerful stimulus for GnRH secretion, administration of kisspeptin offers a method to directly interrogate the function of GnRH neurons in humans, just as GnRH administration has served as a probe of pituitary gonadotrope function in humans for decades. We hypothesize that, in order to respond to kisspeptin with an increase in serum LH, humans must have a certain "threshold" number of GnRH neurons positioned properly within the hypothalamus, adequate GnRH synthetic capacity, and normal secretory mechanisms of GnRH and LH. Thus, in pathophysiologic states that compromise the integrity of the GnRH neurons, the response to kisspeptin would be reduced or attenuated. Therefore, our goal is to use kisspeptin administration as the first direct probe of GnRH neuronal integrity in human reproductive biology to gain new insights into GnRH neuronal function (or dysfunction) in the context of gene variants that impact central regulation of the reproductive axis.

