#### **II. SPECIFIC AIM**

To employ exogenous administration of kisspeptin to directly interrogate human GnRH neurons *in vivo* using GnRH-induced LH secretion as a surrogate marker of adequate GnRH neuronal fate specification, migration, hormone synthesis, secretion, and action.

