#### 3. TCRC Visit:

The general structure of these visits is:

- a period of q10 minute blood sampling without intervention to assess endogenous hormone secretion,
- administration of kisspeptin followed by q10 minute blood sampling to assess the response to kisspeptin, and
- administration of GnRH followed by q10 minute blood sampling to assess the response to GnRH.

These may include the following procedures:

Female subjects will undergo a urine pregnancy test. The results of the pregnancy test
will return prior to any study drug administration and a positive pregnancy test will result
in immediate termination of the study.

- Female subjects with any well-documented method of surgical sterilization will not undergo a pregnancy test
- Frequent blood draws (3-5 mL) every 10 minutes for 12 hours; such that the total amount of blood drawn during the visits does not exceed 550 mL
- Kisspeptin administration of one IV bolus at hour 8
  - o The dose of the kisspeptin bolus will not exceed 13.19 mcg/kg (10 nmol/kg)
- GnRH administration of one IV bolus at hour 11
  - o The dose of the single GnRH bolus will be in the range of 25-75 ng/kg
- EMLA cream may be used to ease discomfort from needle insertion.

Subjects will receive isovolumetric replacement with saline during blood sampling. Kisspeptin will be administered by a TCRC RN or study medical professional. Vital signs (HR, BP, RR, and T) will be measured prior to beginning frequent sampling and at least once every 4 hours during sampling.

Study procedures will be halted if any of the following criteria are met at any point in the study.

- Blood pressure > 180 mmHg systolic or >105 mmHg diastolic at any point during the protocol
- Development or suspicion of an allergic reaction or serious adverse reaction
- Positive pregnancy test
- Temperature ≥101.5°F

Any subject who develops high blood pressure or an allergic reaction will receive medical care until the issue is resolved, with subsequent follow-up as needed.

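### The acceptance rule rests on LH amplitude without reference to the GnRH response, so a difference in pituitary responsiveness could be read as a GnRH-neuron defect

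*Combined protocol and SAP*

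**What the plan says.** **Decision rule.** Under Statistical Design and Power: "The hypotheses will be accepted if subjects at high genetic risk demonstrate reduced endogenous and exogenous kisspeptin-induced LH pulse amplitude", relative to the low-risk group. The response to GnRH is not part of the rule.

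**What acceptance is taken to mean.** The Specific Aim describes "using GnRH-induced LH secretion as a surrogate marker of adequate GnRH neuronal fate specification", and its list continues to synthesis, secretion and action. The first entry under Hypotheses reads: "Patients with a positive but comparatively attenuated response to kisspeptin will have defects in GnRH neuronal fate specification or migration". The second, for Biobank participants, is worded only in terms of endogenous LH pulse amplitude or frequency.

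**What the LH response depends on.** The Background section on probing the GnRH neuron lists, besides enough well-placed GnRH neurons, "adequate GnRH synthetic capacity, and normal secretory mechanisms of GnRH and LH".

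**Who is eligible.** The Inclusion Criteria admit carriers of any variant expected to bear on the function of the reproductive axis. They do not restrict the site at which it acts.

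**The GnRH challenge.** The general structure in section 3, TCRC Visit, ends with "administration of GnRH followed by q10 minute blood sampling to assess the response to GnRH". The procedure list gives "GnRH administration of one IV bolus at hour 11", under the lead-in "These may include the following procedures". Statistical Design and Power is firmer: "Individuals recruited from the Biobank will undergo baseline neuroendocrine LH pulse pattern evaluation, as well as Kisspeptin and GnRH stimulation testing".

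**Planned analyses.** The Data Analysis section covers mean LH, pulse analysis and nadir-to-peak LH amplitude in general terms. It also gives a repeated-measures analysis of FSH and sex steroids in response to kisspeptin. It names no comparison of GnRH-induced LH amplitude between risk groups or against the kisspeptin response.

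**The concern.** Kisspeptin acts on the GnRH neuron, but the measured outcome is LH, one step downstream. A low LH amplitude can arise because less GnRH is released or because the pituitary responds less to it. The rule asks for a reduction under two conditions, endogenous and kisspeptin-stimulated, but both pass through the pituitary. Requiring both therefore gives no protection against a pituitary explanation.

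The protocol does include a test that bypasses the GnRH neuron, and it gives participants a second investigational drug to obtain it. The plan then assigns the result no analytic use. What is at stake is the attribution of a positive finding. The rule accepts the hypotheses in the plural, and the first of them locates the defect in GnRH neurons. If the role of the GnRH response is decided only after the data are seen, any argument from it will be post hoc.

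**Working it through.** **1. The plan's own figure.** The plan gives 25 per group at 80% power by a one-sample exact binomial test. This can be neither reproduced nor refuted, because alpha, sidedness, both proportions and any SD are missing. For orientation, with n = 25 and a null proportion of 0.5, the critical count is 18, the actual alpha is 0.0216, and 80% power needs a true proportion of about 0.77. The dropout figure is close: 50/(1 − 0.15) = 58.8, so 59 against the stated 60. Nothing below depends on these figures except the use of 25 per group.

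**2. What the rule can see.** Let N be the log contribution of the GnRH neurons and P the log pituitary responsiveness. Endogenous and kisspeptin-induced log amplitudes are each N + P, and the GnRH-induced log amplitude is P. A halving is ln(0.5) = −0.69.

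| Shift in high-risk group | Endogenous | Kisspeptin | GnRH | Kisspeptin minus GnRH |
|---|---|---|---|---|
| N halved | −0.69 | −0.69 | 0 | −0.69 |
| P halved | −0.69 | −0.69 | −0.69 | 0 |

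The rule uses only the first two numeric columns, and there the two rows are identical. The rows differ only in the last two columns.

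**3. How often the rule is met.** Simulation: 25 per group, 4,000 trials per setting, log-normal amplitudes. A reduction was counted when a two-sided 0.05 t-test on the log scale was significant in the direction of lower values in the high-risk group. The test is an assumption, since the plan names none for the rule. Assumed SDs for pituitary, neuron and residual components were 0.3/0.3/0.2, 0.4/0.4/0.3 and 0.5/0.5/0.4. The total log-SD is the root of the summed squares, for example √(0.09 + 0.09 + 0.04) = 0.47.

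| Total log-SD | 0.47 | 0.64 | 0.81 |
|---|---|---|---|
| Rule as written, P halved | 99.9% | 94.2% | 78.1% |
| Rule as written, N halved | 99.9% | 94.5% | 76.9% |
| Rule plus lower kisspeptin-to-GnRH ratio, P halved | 2.4% | 2.7% | 2.7% |
| Rule plus lower kisspeptin-to-GnRH ratio, N halved | 99.9% | 93.6% | 72.5% |

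The last two rows show that the GnRH data can discriminate. They are not a proposed decision rule. They also assume that a neuron defect leaves the pituitary response intact, which favours the contrast.

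**4. Precision of the contrast at 25 per group.** The documents give no SD or within-person correlation, so a range is shown. With log-SD σ (taken as equal for the two responses) and correlation ρ, the SD of the log ratio is σ√(2(1 − ρ)), and the 95% CI half-width is 1.96 × that SD × √(2/25).

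| σ | ρ | SD of log ratio | Half-width |
|---|---|---|---|
| 0.47 | 0.5 | 0.47 | 0.26 |
| 0.47 | 0.2 | 0.59 | 0.33 |
| 0.81 | 0.5 | 0.81 | 0.45 |
| 0.81 | 0.2 | 1.02 | 0.57 |

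All four lie below the 0.69 that corresponds to a halving. At the unfavourable end the contrast is not strong. With σ = 0.8 and ρ = 0.2 the SD is 1.01, the standard error is 1.01 × √(2/25) = 0.286, 0.693/0.286 = 2.42, and power is Φ(2.42 − 1.96), about 68%.

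**The case against.** Several stronger readings are tempting, and the documents do not support them.

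- **That a pituitary defect would be reported as a GnRH-neuron defect.** The acceptance sentence names no site. The power section concerns Biobank recruits, whose own hypothesis is about LH only. The aim's list ends with GnRH action, which takes place at the pituitary. The text supports only that it could be so read, through the first hypothesis.
- **That any cause of low LH meets the rule.** The cause must differ between genetic-risk groups and must lower both amplitudes.
- **That every participant receives GnRH.** This is firm for Biobank recruits, but the lead-in to the visit's procedure list is permissive.
- **That the GnRH response goes unmeasured.** The general LH amplitude definition could be applied to it. What is missing is the group comparison and its bearing on the conclusion.
- **That pituitary genes are known to be included.** The eligibility wording leaves room for them, but none is named. The genes the protocol does name are presented as acting through the kisspeptin and GnRH pathway.

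There is also a fair case against making a kisspeptin-to-GnRH ratio a mandatory test. GnRH is given as a range of 25–75 ng/kg and kisspeptin only as a ceiling, so the ratio could vary with dose. GnRH always follows kisspeptin, three hours later, with one hour of sampling left. A log ratio is undefined for a participant with no LH response. Long-standing GnRH deficiency may itself blunt the pituitary, a possibility the documents do not address, and a strict gate could then miss a true hypothalamic defect.

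These objections limit the wording and the form of the remedy. They do not give the present rule any means of separating the two sites.

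**Conclusion.** The point holds as a limit on interpretation. Followed as written, the rule cannot distinguish reduced pituitary responsiveness from reduced GnRH-neuron output. In the illustration the two are accepted at nearly the same rate, within 1.2 percentage points at each assumed SD. The protocol's own account of what an LH response requires makes the pituitary explanation one that must be addressed before acceptance is taken to support the first hypothesis.

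The structural conclusion needs no numerical assumption. The acceptance rates depend on the assumed SDs, a 50% effect, the additive log model and the chosen t-tests. The precision range of 0.26 to 0.57 depends on assumed log-SDs of 0.47–0.81 and correlations of 0.2–0.5. The primary amplitude comparison is not invalid: it remains a sound test of reduced reproductive-axis output. Nor do the documents show that a misattribution will occur.

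**What to change.** Keep the primary amplitude comparison, and add the following to Data Analysis and to Statistical Design and Power before outcome data are examined:

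1. A comparison of GnRH-induced LH amplitude between risk groups, reported as an estimate with a 95% CI, in the participants who received the GnRH bolus. State who these are, reconciling the permissive procedure list with the firm statement for Biobank recruits.
2. A supportive group-by-stimulus contrast of kisspeptin against GnRH response. It should account for the doses actually given and state how participants with no LH response are handled.
3. An amended acceptance sentence. Reduced LH amplitude alone is reported as reduced reproductive-axis output, and attribution to GnRH neurons is made only when the results of items 1 and 2 support it. If both responses fall together, the site is reported as undetermined. The ratio is evidence for interpretation, not a pass/fail gate.

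The cost is a few sentences and an analysis of samples the visit already schedules. The downside is a more cautious claim when both responses are reduced, including in some cases where the defect truly is hypothalamic.
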